#### (2) Accessory examination

- 1) ECG examination: use resting ECG to evaluate arrhythmia and ST-T changes, etc.
- 2) Laboratory tests:

Fasting for more than 6 hours, blood routine, urine routine, fasting blood glucose, alanine aminotransferase, aspartate aminotransferase, blood urea nitrogen, creatinine, plasma total cholesterol, triglyceride, low-density lipoprotein cholesterol, high-density lipid Protein cholesterol, high-sensitivity C-reactive protein, prothrombin time, serum troponin, NT-proBNP.

3) Transthoracic echocardiography:

Two-dimensional dynamic images of left ventricular parasternal long axis, apical fourchamber heart, apical two-chamber heart, apical long axis, left ventricular apex level, papillary muscle level, and mitral valve level short-axis view; measure left ventricular ejection fraction (LVEF); Pulse wave Doppler was used to obtain the diastolic mitral valve orifice blood flow spectrum, and tissue Doppler was used to obtain the mitral valve annulus motion spectrum, and E/e' was calculated; Using speckle tracking imaging (STI) ultrasound technology to measure global longitudinal strain (GLS)/strain rate, global circumferential strain, global radial strain, global area strain (3D-GAS), left ventricular torsion, left ventricular rotation/untwisting speed, systolic dissynchrony index (SDI) and right ventricular free wall systolic peak strain (RVFWS) and so on.

4) Carotid ultrasound examination: the patient was the occipital supine position, with slightly raised jaw, the face was turned to one side, and the sternocleidomastoid muscle was fully exposed. The probe scans from the posterior edge of the sternocleidomastoid muscle to display the long axis and short axis images of the common carotid artery, internal and external carotid arteries, and bifurcation. The intima-media thickness, internal diameter and blood flow velocity were measured at 1-2 cm before the

bifurcation of the common carotid artery.

## (3) The main observation and detection indicators of the first follow-up

Hypertensions will be followed up in the 12th, 24th, 36th and 48th months after being enrolled in this study. They can be followed up through outpatient service or telephone. Each follow-up shall not exceed two weeks before and after the specified follow-up time. Perform physical examination, ECG examination, laboratory examination, echocardiography, etc. Record the treatment and whether there are adverse cardiovascular clinical events (myocardial infarction, heart failure, cardiovascular death, unstable angina requiring hospitalization, aortic aneurysm or aortic dissection, stroke). Record the time when the adverse event occurred.

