## **EFFICACY ASSESSMENT**

Primary study endpoints: emerging atrial fibrillation, transient ischemic attack (TIA) or stroke, unstable angina, myocardial infarction, heart failure, coronary revascularization, cardiovascular death; Secondary study endpoints: decreased cardiac function with preserved ejection fraction; new cardiac remodeling; aortic aneurysm or aortic dissection; ECG showed that QTc (QT interval corrected by heart rate) was more than 500ms or QTc was longer than the baseline level for more than 60ms, emerging torsade de pointes ventricular tachycardia and other serious arrhythmias; the relationship between the deviations of blood pressure within the same day and the difference of cardiac function indexes.

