## **DIAGRAM OF RESEARCH SCHEME**

## **CHART OF RESEARCH SCHEME**

Follow-up time	0 month	12th month	24th month	36th month	48th month
Information	•				
Medical history	•				
Inclusion Criteria	•				
Informed consent	•				
Electrocardiogram	•	•	•	•	•
Physical examination	•	•	•	•	•
Laboratory examination	•				
Echocardiography	•		•		•
Arterial ultrasound	•		•		•
Drugs treatments	•	•	•	•	•
Adverse events		•	•	•	•

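### Follow-up may be by telephone although ECG and examination are required at every follow-up, so new atrial fibrillation, a primary component, is ascertained unevenly

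*Protocol*

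**What the plan says.** - **Follow-up, section (3) on the main observation and detection indicators.** The times are fixed: "Hypertensions will be followed up in the 12th, 24th, 36th and 48th months after being enrolled in this study". The mode is left open: "They can be followed up through outpatient service or telephone". The procedures follow: "Perform physical examination, ECG examination, laboratory examination, echocardiography, etc". The paragraph then lists the events to record: myocardial infarction, heart failure, cardiovascular death, unstable angina leading to admission, aortic aneurysm or dissection, and stroke.
- **Chart of research scheme.** The row "Electrocardiogram" is marked at months 0, 12, 24, 36 and 48, and so is physical examination. Echocardiography is marked only at months 0, 24 and 48, and laboratory tests only at month 0.
- **Efficacy assessment.** "Primary study endpoints: emerging atrial fibrillation, transient ischemic attack (TIA) or stroke, unstable angina, myocardial infarction, heart failure, coronary revascularization, cardiovascular death". One secondary endpoint is defined by the tracing itself: "ECG showed that QTc (QT interval corrected by heart rate) was more than 500ms", or a prolongation of more than 60 ms from baseline.
- **Accessory examination.** The purpose of the tracing is given as "use resting ECG to evaluate arrhythmia and ST-T changes, etc".
- **Statistical treatment, (1) Analysis data set.** The sentence on patients without an observed cardiovascular or cerebrovascular event is garbled. Its natural reading is censoring at the last follow-up date.
- **Statistical treatment, (4) Analysis of main endpoint events.** Cox regression relates ventricular geometry and left atrial enlargement to adverse cardiovascular events.

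**The concern.** The follow-up paragraph permits a type of contact that cannot supply what the same paragraph and the chart require. No section limits telephone contact to certain visits, asks for a later ECG, or says how atrial fibrillation is to be ascertained on a call. The event list does not fill the gap, because a caller who follows it would not ask about atrial fibrillation.

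The study compares event rates between geometry and atrial-size groups, so what is at stake is equal detection of the primary endpoint. A patient reached only by telephone, with atrial fibrillation that no one has recorded, enters the Cox model as event-free up to the call. QTc cannot be ascertained by telephone at all, and neither can new remodeling.

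**Working it through.** **1. Passages side by side.**

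| Item | Follow-up paragraph | Chart | Possible by telephone? |
|---|---|---|---|
| ECG | required | months 12, 24, 36, 48 | no |
| Physical examination | required | months 12, 24, 36, 48 | no |
| Echocardiography | required | months 24, 48 | no |
| Laboratory tests | required | baseline only | no |

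Of the seven items in the primary endpoint, three are absent from the list of events to record: atrial fibrillation, TIA and coronary revascularization.

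**2. The plan's own figure.** The sample size section gives event rates of 4.9% and 2.2%, two-sided alpha 0.05 and 986 per group, with no power stated. The two-proportion formula without continuity correction gives 985 per group at 90% power, and power at 986 is 0.900. The plan therefore implies 90% power. It expects 986 × 0.049 = 48.3 and 986 × 0.022 = 21.7 events, and a risk ratio of 4.9/2.2 = 2.23.

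**3. Equal telephone use in both groups.** The protocol gives none of the next three inputs, so they are assumptions: atrial fibrillation is s = 10-30% of events, telephone use is t = 10-50%, and m = 25-100% of telephone patients' atrial fibrillation is missed. The share of events lost is s × t × m.
- Smallest: 0.10 × 0.10 × 0.25 = 0.25%. Power stays at 90.0%, and n for 90% power is 988 per group.
- Largest: 0.30 × 0.50 × 1 = 15%. Power falls to 84.6%, and n for 90% power is 1166 per group.

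Both rates shrink by the same factor, so the ratio of 2.23 is unchanged.

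**4. Unequal use, atrial fibrillation alone, no true difference.** Let f be the share of atrial fibrillation found only on a study ECG (assumed 30-70%). Spurious ratio = (1 − f × t_LVH)/(1 − f × t_nonLVH).
- Telephone 10% (LVH) versus 30% (non-LVH): 0.97/0.91 = 1.07; 0.95/0.85 = 1.12; 0.93/0.79 = 1.18, for f = 0.3, 0.5 and 0.7.
- Reversed, 30% versus 10%: 0.91/0.97 = 0.94 to 0.79/0.93 = 0.85.

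**5. Unequal use, composite, 10% versus 30%.**
- If s is the share of all true events: (1 − s f × 0.10)/(1 − s f × 0.30). At s = 0.1, f = 0.3: 0.997/0.991 = 1.006. At s = 0.3, f = 0.7: 0.979/0.937 = 1.045.
- If s is the share of recorded non-LVH events: 1 + s × (ratio − 1), which gives 1.007 to 1.053.

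Either way the range is about 1.01 to 1.05.

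**6. Effect on the planned ratio** (atrial fibrillation 20% of events, half missed in telephone patients).
- Telephone 50% in LVH, 10% in non-LVH: 0.04655/0.02178 = 2.14.
- Telephone 10% in LVH, 50% in non-LVH: 0.04851/0.02090 = 2.32.

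The sign depends on which group is telephoned more.

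**The case against.** The strongest reply is that the textual inconsistency needs one clarifying sentence and that more is easily read into it than it holds. Much of this stands.

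- **Direction.** A reader might infer that patients with hypertrophy or atrial enlargement attend clinic more often, so that hazard ratios are pushed away from 1. No section says so, and steps 4 and 6 give either sign.
- **Size.** A reader might take 1.07-1.18 as the impact on the primary result. It applies to one of seven items, under assumed inputs. The composite figure is about 1.01-1.05, against a planned ratio of 2.23.
- **Missed for good.** The formulas treat a telephone patient as never having an ECG. With four annual contacts, a later clinic ECG can still find sustained atrial fibrillation, and cases diagnosed in routine care can be reported by telephone. The loss is partly delay.
- **QTc and remodeling.** A reader might extend the censoring sentence to these secondary endpoints. It covers adverse cardiovascular and cerebrovascular events, and no time-to-event rule is stated for the others. Under the chart, a clinic visit at month 12 or 36 would not detect new remodeling either.
- **Left to the SAP.** Sensitivity analyses can be specified there. Contact mode, visit procedures and the event list are protocol content, and no later analysis can recover an ECG that was not taken or a contact mode that was not recorded.

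These points limit size and sign. They do not remove the contradiction or the incomplete event list, which needs no assumption about telephone use.

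**Conclusion.** The point holds as a contradiction with a gap in ascertainment. Telephone contact is allowed at any follow-up, the required procedures cannot be done by telephone, and nothing says how new atrial fibrillation is ascertained on a call. Atrial fibrillation that only a study ECG would find can be missed or found late in these patients. Reading the garbled analysis-set sentence as censoring at last follow-up, they count as event-free up to the call.

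Equal use mainly costs events and power: 0.25-15% of events, and power between 90.0% and 84.6% under the assumed ranges. Unequal use biases the hazard ratio in a direction the protocol does not settle, by about 1.01-1.05 on the composite in the 10% versus 30% case, or below 1 if the imbalance is reversed. The protocol gives no telephone share, no atrial fibrillation share and no share found only on ECG, so every size here is illustrative.

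**What to change.** 1. Reconcile the follow-up paragraph with the chart: state which contacts, if any, may be by telephone and which procedures each contact must include.
2. Align the list of events to record with the primary endpoint, so that every contact, calls included, asks about atrial fibrillation, TIA and coronary revascularization.
3. Record the mode of each contact and whether an ECG was done.
4. Keep the primary composite on all contacts. Censoring the whole composite at the last ECG would discard infarctions, strokes and deaths reported later by telephone.
5. Add two sensitivity analyses: the composite without atrial fibrillation detected only on a study ECG, and atrial fibrillation alone, censored at the last contact with an ECG.
6. Assess QTc and new remodeling only in patients who had the relevant ECG or echocardiogram.

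Cost: one or two CRF fields, a longer event checklist, one or two sensitivity analyses, and slightly less follow-up time in the analysis of atrial fibrillation alone.

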#### **RESEARCH PLAN**

#### **Estimation of Sample Size**

Use PASS 11.0.7 software, bilateral inspections,  $\alpha = 0.05$ , with the incidence rate of cardiovascular adverse events in the left ventricular hypertrophy group was 4.9%, and the incidence rate of cardiovascular adverse events in the left ventricular non-hypertrophy group was 2.2%, at least 986 hypertensive patients were included in the left ventricular hypertrophy group and the left ventricular non hypertrophy group, respectively. Considering the 10% loss rate, at least 1085 patients were included. With 20 research centers, we planned to collect at least 110 patients with hypertension (including 55 patients in left ventricular hypertrophy group), 5-10 healthy volunteers (aged 30-60 years) in each center. Then 2200 patients with hypertension in total, and 100 healthy volunteers will be selected in this study.

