#### (4) Analysis of main endpoint events:

1) Cox regression was used to analyze the predictive value of different types of left ventricular remodeling and left atrial enlargement on adverse cardiovascular events. ROC analysis was used to compare the incremental effect of left ventricular remodeling, left ventricular hypertrophy and left atrial enlargement on the predictive ability of hypertensive cardiovascular events; NRI [net corrected classification, i.e. (new sensitivity + new specificity) - (old sensitivity + old specificity)] was used to evaluate and compare the ability

of left ventricular remodeling, left ventricular hypertrophy and left atrial enlargement to re stratify and optimize the risk of cardiovascular events in hypertension. Multivariate regression analysis was used to analyze the factors affecting left ventricular remodeling and left atrial enlargement in hypertension.

2) The incidence time of adverse cardiovascular events was stratified by left ventricular remodeling, left ventricular hypertrophy and left atrial enlargement. Cox regression analysis was used to calculate the hazard ratio and its bilateral 95% confidence interval of different influencing factors.

(5) Statistical software: SAS 9.4 or SPSS software was used for analysis. Bilateral tests were used for statistical tests.  $P \le 0.05$  were considered statistically significant.

(6) Interim analysis: No interim analysis will be conducted in this study. If special cases occur, the main research center, researchers and statistical experts will discuss and decide.

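### The events sites are told to record at follow-up do not match the primary endpoint: new atrial fibrillation, TIA and coronary revascularization are missing, and unstable angina is limited to hospitalized cases

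*Protocol*

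**What the plan says.** The Efficacy Assessment section of the protocol defines the primary endpoint: "Primary study endpoints: emerging atrial fibrillation, transient ischemic attack (TIA) or stroke, unstable angina, myocardial infarction, heart failure, coronary revascularization, cardiovascular death". Unstable angina carries no hospitalization condition there. The same sentence places "new cardiac remodeling; aortic aneurysm or aortic dissection" among the secondary endpoints.

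Under Research Plan, item (3) on follow-up, sites are told to record the treatment, any "adverse cardiovascular clinical events (myocardial infarction, heart failure, cardiovascular death, unstable angina requiring hospitalization, aortic aneurysm or aortic dissection, stroke"), and the time of each event. Contacts fall at months 12, 24, 36 and 48. On how they are made, the section says: "They can be followed up through outpatient service or telephone".

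Elsewhere the wording is generic:

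- The Chart of Research Scheme has a single row for adverse events.
- The sample-size section says only that "the incidence rate of cardiovascular adverse events in the left ventricular hypertrophy group was 4.9" (per cent), against 2.2% without hypertrophy.
- Under Statistical Treatment, item (4), "Cox regression was used to analyze the predictive value of different types of left ventricular remodeling and left atrial enlargement on adverse cardiovascular events". The components are not restated.

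**The concern.** The analysis of the main endpoint depends on what sites were told to collect. The Cox model needs each primary event with its date, and the ROC and net reclassification analyses need complete event status. If the collection instruction is narrower than the endpoint, some primary events may never be recorded, or may be recorded in some of the 20 centres and not in others. A statistical analysis plan cannot repair this later, because it can define the analysis endpoint but cannot recover events and dates that were not collected.

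The stake is precision and consistency across centres. There is no ground in the protocol to suppose that events would be lost more often in one hypertrophy group than in the other, so a biased hazard ratio is not claimed.

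**Working it through.** **1. The two lists side by side**

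| Component | Efficacy Assessment | Recorded and dated at follow-up |
|---|---|---|
| Myocardial infarction | primary | yes |
| Heart failure | primary | yes |
| Cardiovascular death | primary | yes |
| Stroke | primary | yes |
| Unstable angina | primary, no condition | only if hospitalized |
| New atrial fibrillation | primary | not listed |
| TIA | primary | not listed |
| Coronary revascularization | primary | not listed |
| Aortic aneurysm or dissection | secondary | yes |

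Four components match exactly, three are absent, one is narrowed, and one listed item belongs to the secondary endpoints. The follow-up list is therefore neither the primary endpoint nor a subset of it. It also has no open-ended closing term, whereas the sentence before it, on examinations, ends with one. Read literally, it is a closed list.

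**2. The plan's own sample size**

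Inputs from Estimation of Sample Size: p1 = 0.049, p2 = 0.022, two-sided alpha 0.05, 986 per group. Power is not stated, so it was solved for. The two-proportion formula with pooled null variance is

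n = [1.960·√(2·p̄·(1−p̄)) + z_power·√(p1(1−p1) + p2(1−p2))]² / (p1−p2)²

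With p̄ = 0.0355 and 90% power (z = 1.2816):

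n = [1.960 × 0.2617 + 1.2816 × 0.2610]² / 0.027² = 0.7180 / 0.000729 ≈ 985.

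The stated 986 is reproduced to within one patient, so 90% power is implied. For comparison, 80% power would give 737 and 95% would give 1,218.

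**3. What under-recording would cost (illustration)**

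The protocol plans 2,200 patients, 1,100 per group. After 10% loss, 1,100 × 0.9 = 990 per group are evaluable, and 990 × (0.049 + 0.022) = 70.3 events are expected. Suppose that the two rates describe the full primary list and that a share f of events is missed equally in both groups, so both rates are multiplied by 1 − f. Then

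power = Φ{ [(p1−p2)·√990 − 1.960·√(2·p̄·(1−p̄))] / √(p1(1−p1) + p2(1−p2)) }

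and the implied hazard ratio is ln(1−p1)/ln(1−p2).

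| Share missed | Events | Power | Implied hazard ratio |
|---|---|---|---|
| 0 | 70.3 | 90.1% | 2.258 |
| 10% | 63.3 | 86.8% | |
| 20% | 56.2 | 82.5% | |
| 30% | 49.2 | 77.1% | 2.249 |
| 50% | 35.1 | 62.4% | 2.243 |

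Power falls to 80% when about 25% of events are missed. With 986 per group the figures are almost the same (90.0%, 86.7%, 82.4%, 76.9%, 62.2%; 80% power at 24.6% missed).

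**The case against.** The best case for the protocol is that other provisions could catch the missing events.

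- **ECG.** A resting ECG is scheduled at every visit, and the protocol says to "use resting ECG to evaluate arrhythmia and ST-T changes, etc". This may find some atrial fibrillation. A single tracing gives no onset date, however, and is not available at a telephone contact. That a yearly ECG can miss episodes between visits is a limit of the schedule. Adding atrial fibrillation to the list would not change it, though it would prompt sites to ask about diagnoses made since the last contact and to date them.
- **Treatment records and the adverse-event row.** These could reveal a revascularization or a TIA. Neither names these events or asks for them explicitly, so capture would depend on how each centre reads the protocol.
- **The case report form.** Electronic Data Management says it is built from the whole research scheme, so it may already include every primary component. It is not shown, and the mismatch could equally have been carried into it.
- **Wider wording and central review.** The full analysis set refers to cerebrovascular as well as cardiovascular events, which could cover TIA but does not name it. An event committee appears in the publication plan only, with no described role, and it can judge only what is reported.
- **Unstable angina.** The hospitalization condition may be intended as the working criterion for the primary component. That is plausible, but the protocol then needs to say so in both places.

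The objection to the power figures largely stands. The shares missed have no source in the documents. If patients count once in a composite, a patient with both an omitted and a listed event is still counted, so patient-level loss would be smaller than the omitted components' share of all events. The table shows sensitivity and does not estimate the loss. None of these points makes the two lists agree.

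**Conclusion.** The point holds. The primary endpoint and the instruction for collecting it disagree in the text, and no other section reconciles them. This should be fixed.

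That conclusion needs no assumption. The effect on the results does. How many events would be lost is unknown while the case report form is unseen. The power loss in the illustration assumes that the 4.9% and 2.2% cover the full primary list and that events are missed equally in both groups. On those terms, missing up to about a quarter of events keeps power at or above 80%, and missing half reduces it to about 62%. If the rates describe the follow-up list instead, there is no loss against the planned power, but the primary endpoint as defined would still be incompletely collected. With equal loss the hazard ratio is almost unchanged, so the harm lies in precision and in possible unevenness between centres.

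**What to change.** - Align the Efficacy Assessment section and the follow-up section. Add new atrial fibrillation, TIA and coronary revascularization to the events recorded, with dates, at every contact, including telephone contacts.
- Use one definition of unstable angina in both sections.
- Keep aortic aneurysm or dissection on the recording list, marked as a secondary endpoint.
- State in the sample-size section which event list the 4.9% and 2.2% cover.
- Check the case report form against the aligned list. Where it lacks a component, query the completed visits for that component. Where it already holds all of them, no back-query is needed.

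The cost is an amendment to the protocol wording and, if needed, to the form. Back-queries, if the check shows a gap, could reach up to 2,200 patients in 20 centres, so the check should come first. No extra patients or procedures are required.

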#### Standard operation procedure of echocardiography and carotid ultrasound

#### (1) Personnel requirements:

The ultrasonic inspection personnel must be trained and have the qualification certificate to undertake the ultrasonic inspection of the research project. One or two ultrasonic examiners in the same research center will be fixed to participate in this study. All data shall be stored by DVD or hard disk in DICOM format. Each patient is a folder, including each image acquisition time and operator. The image information is sent by the person in charge of each center to the central laboratory via email for summary and storage, and then measured by two experienced ultrasound physicians through offline analysis software. Each data is measured three times and averaged data are stored. The data with poor image quality will be reviewed by professionals, analyzed repeatedly, and finally decided whether to use.

